## Subject Participation:

### Aim 1

Participants will remain in the study for 3 months. Participants will test the app prototype with the proposed refined features for a 2-wk period prior to Focus Group 1. At least 3 focus groups will be convened over a 3-month period. Each session (up to 90 minutes) will be led by a trained moderator from the Mayo Clinic Qualitative Research Center, will be audio-recorded and transcribed. A co-moderator (either another moderator from the Mayo Clinic Qualitative Research Center or the study PI) will record field notes and manage room equipment. The discussion will follow a semi-structured moderator guide, informed by preliminary studies and the Health Information Technology Usability Evaluation Model/Scale (Health-ITUDEM/Health-ITUES), on app prototype features, proposed revisions, and LS7 incorporation. The Health-ITUDEM and Health-ITUES are systematic rubrics for evaluating mHealth intervention usability, particularly for health-related apps. Questions will be structured by category and sessions will integrate attentiveness to AA faith community cultural norms and values. The series will inform sequential revisions of the app prototype components by the study team and software developers (CareHubs, Inc.) for review at subsequent focus groups.

Focus groups will be held at local churches, community venues and Mayo Clinic. As an alternative to the face-to-face focus groups, we have outlined potentially two strategies to receive feedback from participants: 1) virtual focus groups will be held (via an online meeting platform such as Zoom, Go-To-Meeting, etc.) or 2) semi-structured interviews to participants individually will be conducted by the trained moderator from the Mayo Clinic Qualitative Research Center.

## Aim 2

Participants will remain in the study for 18 months: Intervention phase (2.5 months each/group, total 5 months), Maintenance phase (6 months each/group, total 12 months). Participants will then complete a baseline electronic survey and health assessment. Two 1-hour, hands-on instructional training sessions on the app login process, basic features and navigation will be delivered by the study team (1 each in Rochester and MSP). Participants will be provided with a step-by-step instructional manual to support independent use.

**Schedule of Assessments**

Data Collected	# Items	Baseline	Immediate Post-intervention	6 months
Sociodemographics				
eHealth literacy: eHEALS 	10	X		
Mobile technology use skills 	13	X		
CV health (LS7) measures				
BP	--	X		X
Fasting lipid panel	--	X		X
Fasting glucose	--	X		X
Height/weight (BMI)	--	X		X
Cigarette smoking status	--	X		X
Diet quality: Delta Nutrition Intervention FFQ 	158	X	X	X
PA patterns: International PA Questionnaire 	7	X	X	X
Feasibility measures				
App engagement	--		X	X
App usability 	20		X	X
Psychosocial measures				
Diet/PA self-efficacy 	12/12	X	X	X
Diet/PA self-regulation 	16/10	X	X	X
Diet/PA social support 	10/13	X	X	X
Religiosity/spirituality: Daily Spiritual Experiences Scale 	6	X		X
Optimism: Life Orientation Test-Revised 	6	X		X
Perceived stress: Global Perceived Stress Scale 	8	X		X

**Randomization (Figure 2).** We will use a cluster RCT design with 2 waves of implementation inclusive of 2 groups: intervention (Group 1) and delayed intervention (Group 2, control group). We will randomize clusters of churches in Rochester and MSP to receive the intervention immediately following baseline health assessments including LS7 measures (Time 1, Group 1) or at post-maintenance (Time 3, Group 2). Groups 1 and 2 will complete post-intervention assessments by electronic survey of CV health behaviors, feasibility and psychosocial measures (Times 2 and 4). Both groups will complete a second health assessment at post-maintenance (Time 3), to allow for comparison of LS7 measures between Groups 1 and 2. Times 4 through 5 are data collection points following the intervention (post-intervention and post-maintenance) for Group 2. The study statistician will randomize churches, ensuring the number of participants in Groups 1 and 2 is balanced. Churches will be told their group assignment after baseline assessments.

[figure not shown]

Figure 2. RCT with delayed intervention

**Baseline and 6 month Health Assessment:** Enrolled and consented participants will then complete a baseline assessment with screening of CVD risk profiles. CVD risk profiles will be assessed by measurement of height (without shoes to the nearest centimeter by a stadiometer), weight (using a calibrated scale in kilograms), blood pressure (average blood pressure of three sitting readings with an oscillometric automated device), lipid panel (by Cholestech system fingerstick measurement), random glucose (by fingerstick measurement).

**Optional Group Meeting Following Maintenance:** 15 participants from both Group 1 and Group 2 will be selected on a first-come, first-serve basis to participate in an optional group meeting, lasting about 2-hours, to be conducted at the post-maintenance phase. Participants will provide more information about the program and how it could be changed or improved.

**Intervention condition.** The app-based intervention is an individually-tailored program to promote LS7 through health education to increase awareness and skill development while enhancing self-efficacy, self-regulation, and social support for healthy behavior change. The app includes a 10-wk core series of multimedia education modules with a LS7 focus and other features including interactive self-quizzes, self-monitoring (diet/PA), and social networking (sharing board). The intervention is intended for participants to follow a weekly schedule of each module concentrating on each LS7 component. Personalized messages guided by the theory-based models (PAPM, SEM) will be delivered to each participant 3-4 times weekly over the intervention phase through the app dashboard and by text message or email as per participant preferences. Messages will be either informational, cues to action, reminders or motivational/praise for healthy behavior change. The sharing board will be moderated weekly by Mayo Social Media with posts to foster discussion on behavior change influences (barriers, facilitators) and participant successes/challenges to healthy lifestyle. Moderated posts will include messages, videos and images from reputable sources (eg, AHA, Mayo) and those cultural relevant to the AA faith community. Participants will be notified of new posts via the app homepage. Participants will maintain app access for the duration of the study.

**Control condition (Delayed intervention group).** The delayed intervention group will not receive additional materials while under the “control” timepoint (intervention group within intervention/maintenance phases).

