### Preliminary Work:

- I. **Using CBPR to design and test FAITH! intervention.** The original focus of the FAITH! (Fostering African-American Improvement in Total Health) Program was chronic disease prevention through nutrition education. Through formative development in partnership with an AA church in Baltimore, MD, the behavioral theory-based multicomponent intervention included 2 face-to-face education sessions on healthy eating with health professional-led, evidence-based lectures, videos, cooking demonstrations (demos), and culturally tailored, spiritually-motivating, educational materials. **Key Findings:** We enrolled 27 AA adults (74% women, mean age 50). Over the study course, there was a >20% increase in participants reporting  $\geq 5$  fruit/vegetable intake/day (17% baseline, 40% 6-months post-intervention) and a 10% increase in healthy diet self-efficacy. A sustainable, church-run healthy food pantry was also established. **Relevance to Proposed Work:** A CBPR approach with an AA church congregation to jointly develop our evidence-based intervention is feasible and can influence health behaviors.
- II. **Adapting FAITH! intervention to CV health focus among new community partners.** In 2013, we began to build a rich and dynamic CBPR academic-community partnership with 6 predominantly AA churches within Rochester and Minneapolis-St. Paul (MSP), MN. It was mutually agreed upon by our study team and community partners to better address health disparities within the AA faith community by shifting the FAITH! Program's focus to CV health promotion through the LS7 framework, maintaining key intervention components (C1a, face-to-face education sessions). Supportive educational and social support resources included an NHLBI CVD prevention for AAs manual and heart healthy

[figure not shown]

Figure 1: FAITH! App Prototype Homepage

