### **Subject Information**

*Target accrual is the proposed total number of subjects to be included in this study at Mayo Clinic. A "Subject" may include medical records, images, or specimens generated at Mayo Clinic and/or received from external sources.*

**Target accrual:** 215 participants

Aim 1: 15 participants

Aim 2: 16 churches, 200 participants

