## **Power Statement:**

### **Aim 1**

**Not applicable.**

### **Aim 2**

The primary outcome will be a comparison of average change in the AHA LS7 score from baseline (Time 1) to 6-months post-intervention (Time 3) between Groups 1 and 2. Based on our prior study of 37 participants, including 5 churches, the intracluster correlation (ICC) of this outcome was near zero (<0.01), and the coefficient of variation (CoV) of church sizes was 0.38 (average number of participants/church, 10; SD 3.8; CoV 0.38). Assuming similar ICC (0.01) and slightly higher CoV (0.50) since more churches will be included in the planned study, including a total of 16 churches with an average of 10 participants/church, 80 participants/group will provide 85% power to detect a difference of 1.0 in average LS7 score change between the groups (SD 2; effect size 0.50; 5% type-I error rate). The clinical significance of this 1-unit difference in LS7 score is based on a recent meta-analysis demonstrating that each unit increase in LS7 metrics is associated with an estimated 19% and 11% reduction in CVD and all-cause mortality respectively. We will recruit 200 participants to ensure 160 completers (assuming 20% attrition rate).

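### Sixteen churches in two cities are randomised with balance on participant numbers only, so a marked chance imbalance by city is possible and the planned t-test would not correct it

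*Combined protocol and SAP*

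**What the plan says.** The paragraph on randomisation (Figure 2), under Schedule of Assessments, makes churches the unit: "We will randomize clusters of churches in Rochester and MSP to receive the intervention immediately following baseline health assessments". The only restriction it states is "The study statistician will randomize churches, ensuring the number of participants in Groups 1 and 2 is balanced". It does not say that churches are randomised within each area. No other section mentions stratification, matching, minimisation or constrained randomisation on any church characteristic.

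Subject Information gives the size as "Aim 2: 16 churches, 200 participants". The Aim 2 Power Statement works with completers, "including a total of 16 churches with an average of 10 participants/church", and concludes that "80 participants/group will provide 85% power to detect a difference of 1.0 in average LS7 score change between the groups". Its clustering inputs are "Assuming similar ICC (0.01) and slightly higher CoV (0.50) since more churches will be included in the planned study", with an SD of 2.

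The Aim 2 Data Analysis Plan compares average change between the groups with 2-sample t-tests. It names no term for city or church.

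**The concern.** City is known for every church before allocation, and the study is partly organised by it: kickoff events are held separately in Rochester and MSP, and so are the app training sessions. Balancing head counts does nothing to spread cities between arms. With eight churches per arm, chance cannot be relied on to do it either.

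If LS7 change differs between the two areas for reasons unrelated to the app, an uneven split adds that difference to the observed arm contrast, and an unadjusted comparison leaves it there. At stake are the precision of the primary contrast and its standing with readers, who could attribute either a positive or a null result to geography. Allocation happens once, so this is best settled beforehand.

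**Working it through.** **Inputs.** From the documents: 16 churches; 80 completers per group; mean 10 per church; ICC 0.01; coefficient of variation (CoV) of church size 0.50; SD 2; target difference 1.0; 5% type-I error (taken as two-sided). Assumed: eight churches per arm (80 per group divided by 10 per church), and K, the number of Rochester churches, taken as 4, 5 or 6 because the documents do not give it.

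**1. The plan's own figure.** Design effect = 1 + ((0.50² + 1) × 10 − 1) × 0.01 = 1.115. Effective n per arm = 80 / 1.115 = 71.75. Standard error of the difference = 2 × √(2 / 71.75) = 0.334. Power = Φ(1.0 / 0.334 − 1.96) = 0.850. The stated 85% reproduces, and the missing stratification does not alter it.

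**2. Chance of a marked city imbalance.** There are C(16, 8) = 12,870 equally likely 8:8 allocations. The number of Rochester churches in one arm is hypergeometric. Counting allocations in which the arms differ by three or more Rochester churches, in either direction:

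| K | Splits counted | Allocations | Probability |
|---|---|---|---|
| 4 | 4-0 | 990 | 7.7% |
| 5 | 4-1, 5-0 | 3,630 | 28.2% |
| 6 | 5-1, 6-0 | 1,530 | 11.9% |

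**3. Does the stated rule help?** Church sizes were simulated 100 times (mean 12.5 = 200/16, CoV 0.50), keeping only 8:8 allocations whose arm totals differed by no more than 5% of all participants. The probabilities become 7.8%, 28.4% and 11.6%. Balancing participant numbers gives essentially no protection on city.

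**4. How large a city difference the plan's own values allow.** Total between-church variance = ICC × SD² = 0.01 × 4 = 0.04. A city difference of g points, with a fraction p = K/16 of churches in Rochester, contributes g² × p(1 − p). If city explained all of the 0.04, then g = 0.2 / √(p(1 − p)):

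- K = 4: 0.2 / √0.1875 = 0.46
- K = 5: 0.2 / √0.2148 = 0.43
- K = 6: 0.2 / √0.2344 = 0.41

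**5. Resulting shift.** With churches of equal size, shift = g × (difference in Rochester churches) / 8. These are upper limits, because they give city all of the between-church variance.

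- K = 5, split 4-1 (probability 25.6%): 0.43 × 3/8 = 0.16
- K = 6, split 5-1 (11.2%): 0.41 × 4/8 = 0.21
- K = 4, split 4-0 (7.7%): 0.46 × 4/8 = 0.23
- The rarest splits, 5-0 of 5 (2.6%) and 6-0 of 6 (0.7%): 0.43 × 5/8 = 0.27 and 0.41 × 6/8 = 0.31

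The 4-1 shift of 0.16 is about half of one standard error (0.16 / 0.334 = 0.48).

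**The case against.** The strongest reply is that the plan's evidence points to churches hardly differing in LS7 change. The ICC observed in the prior study was below 0.01, and no section shows that city predicts change. The outcome is change from baseline, so stable differences in level between cities cancel. The evidence that city matters is logistical: kickoff events precede allocation, training is short and given by the same study team, and the intervention is a common app. Entry is limited to churches at one readiness stage and to participants with low fruit/vegetable intake and low activity. The trial is described as one of feasibility and preliminary efficacy. Figure 2 is not shown and could carry strata.

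Much of this stands, and it limits the size of the point. It does not remove it. The ICC comes from 37 participants in 5 churches and is imprecise. Entry restrictions narrow heterogeneity but do not balance arms. The text describing Figure 2 names no strata.

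Four stronger readings are tempting, and the documents do not support them:

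- **That the design is biased.** Chance imbalance under randomisation averages to zero over allocations and is equally likely to favour either arm.
- **That imbalance is more likely than not.** Any departure from an even split has probability 57% for K = 4 and 61% for K = 6, but 49 percentage points of each are mild 3-1 or 4-2 splits. Even at the upper limits above, those shift the contrast by only 0.46 × 2/8 = 0.12 or 0.41 × 2/8 = 0.10 points.
- **That cities might differ by 0.5 points.** For K = 4 to 6 this needs between-church variance of 0.25 × p(1 − p) = 0.047 to 0.059, more than the 0.04 the plan allows for all causes together.
- **That prior FAITH! partnership is an equally firm concern.** The protocol describes a "partnership with 6 predominantly AA churches within Rochester and Minneapolis-St. Paul (MSP), MN", but does not say how many will enrol. The existing contacts used for recruitment are Community Steering Committee members, drawn from diverse community organisations, so recruiting through them does not show that enrolled churches are earlier partners.

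**Conclusion.** The point holds as a cheap design improvement, not as a demonstrated flaw. The stated rule leaves a chance of about 8% to 28%, for 4 to 6 Rochester churches out of 16, that the arms differ by three or more Rochester churches, and the planned comparison would not adjust for it. Under the plan's own variance inputs, a 4-1 split moves the contrast by at most about 0.16 points against a target of 1.0; the less likely, more extreme splits move it further, as shown above.

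This rests on an 8:8 split of churches, churches of equal size for the shift, an assumed number of Rochester churches, and an ICC no larger than 0.01. A larger true ICC would raise the limits. Whether city affects LS7 change at all is not known from the documents.

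**What to change.** Randomise churches separately within Rochester and MSP, keeping the balance on participant numbers as a constraint. With an 8:8 split overall, the arms can then differ by no Rochester church if K is even and by one if K is odd, so a difference of three or more cannot occur. If allocation within area is already intended, the protocol should say so.

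For the primary comparison, replace the unadjusted t-test with a church-level analysis or a mixed model with a random church effect, including city as a fixed term. This is a change of primary method, not an added covariate, because the plan contains no model to extend.

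Sample size need not change for the stratification. City uses one of about 14 church-level degrees of freedom (16 churches less 2 arms), leaving 13. Separately from city, the stated 85% corresponds to a participant-level reference distribution; with the same design effect and a t reference on 14 degrees of freedom, power is about 79.5%. The power statement should be updated to match whichever analysis is adopted.

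Prior FAITH! partner status can be added as a further balancing constraint if enough partner churches enrol. This is optional: with 16 churches, the city-by-partner cells may be very small and may compete with the participant-number constraint.

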#### **Biospecimens – Categories 2 and 3**

(2) Collection of blood samples. When multiple groups are involved copy and paste the appropriate section below for example repeat section b when drawing blood from children and adults with cancer.

- a. **From healthy, non-pregnant, adult subjects who weigh at least 110 pounds.** For a minimal risk application, the amount of blood drawn from these subjects may not exceed 550ml in an 8 week period and collection may not occur more frequently than 2 times per week.

Volume per blood draw: Fingerstick blood sample only (per lipid panel, glucose sample)

Frequency of blood draw (e.g. single draw, time(s) per week, per year, etc.) Once at baseline assessment and 6-months follow-up assessment

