### **Aim 2**

Study measures will be summarized and compared between groups using  $\chi^2$  tests for categorical variables and 2-sample *t*-tests for continuous variables. Differences between baseline and each follow-up will be calculated for continuous measures. These differences will be examined overall and within each group, with paired *t*-tests. The average change from baseline will be compared between intervention and control groups with 2-sample *t*-tests. The distribution of categorical outcomes (eg, LS7 component category: poor, intermediate, ideal) will be compared between baseline and each follow-up with McNemar's tests. All variables will be assessed and reported by sex.

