### Aim 2: RCT

#### LS7 score

The LS7 score will be assessed by measurement of BP (average of 3 sitting readings), fasting lipid panel and glucose (by fingerstick), height (to nearest centimeter by stadiometer), weight (with calibrated scale in kilograms), self-reported cigarette smoking status (former, current, never), dietary quality (according to AHA guidelines by validated, culturally appropriate, food frequency questionnaire-FFQ), and PA patterns (minutes/wk of moderate and vigorous intensity PA). LS7 component criteria are adapted from AHA standards based on health assessment data. We will calculate a LS7 score as a composite of each LS7 component by assigning 2-pts for ideal, 1-pt for intermediate, or 0-pts for poor. The total sum will allow for a continuous measure of CV health ranging from poor to ideal (0-14 points). For ease of translation and understanding, the LS7 score will be categorized as 0-6 (poor), 7-8 (intermediate), and 9-14 (ideal).

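### Glucose is random in the visit procedure but fasting in the assessment schedule and LS7 definition, leaving one component of the primary score without a single collection condition

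*Combined protocol and SAP*

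**What the plan says.** Four places in the combined protocol and SAP describe the glucose sample.

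- The paragraph headed Baseline and 6 month Health Assessment describes what staff do at the visit (stadiometer, scale, BP device, lipid analyser). For glucose it gives "random glucose (by fingerstick measurement". It states no fasting condition for the lipid panel.
- The Schedule of Assessments, under the LS7 measures, has a row "Fasting glucose" marked at baseline and at 6 months. The lipid row also says fasting.
- The LS7 score definition, under the primary endpoints for Aim 2, builds the score from "fasting lipid panel and glucose (by fingerstick" together with BP, height, weight, smoking, diet and physical activity. Components are graded by "assigning 2-pts for ideal, 1-pt for intermediate, or 0-pts for poor" and summed to a total of 0 to 14.
- Biospecimens – Categories 2 and 3 gives "Fingerstick blood sample only (per lipid panel, glucose sample" once at each of the two assessments and does not mention fasting state.

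The Power Statement makes the between-group comparison of mean LS7 change from Time 1 to Time 3 the primary outcome. The Aim 2 analysis plan also tests change within groups ("These differences will be examined overall and within each group") and compares component categories between visits ("The distribution of categorical outcomes (eg, LS7 component category: poor, intermediate, ideal"). Under Randomization, "Churches will be told their group assignment after baseline assessments".

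**The concern.** Random and fasting are different conditions for collecting the same sample. The visit paragraph and the LS7 definition list the same physical measurements, so these are two descriptions of one procedure and they disagree.

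If random values are collected and then graded as fasting values, some participants could be placed in the wrong glucose category. There are four possible consequences:

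- **Noise and dilution.** Even if fasting state is the same in both groups, misgrading adds noise to the primary comparison and can dilute a true effect on glucose.
- **Between-group bias.** The comparison of change would be biased if fasting state differed by group at Time 3, which is measured after churches know their assignment.
- **Within-group bias.** The paired tests would be biased if fasting state differed between baseline and 6 months.
- **Category comparison.** When the glucose categories are compared on their own, the other six components do not dilute the misgrading.

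If fasting state is not recorded at collection, it cannot be reliably recovered afterwards.

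**Working it through.** **1. Do the passages describe the same sample at the same visits?** The heading of the procedure paragraph names baseline and 6 months, and the schedule marks its glucose row at those two visits. The LS7 definition names no visits, but the Aim 2 design text and the Power Statement tie the score to them. The schedule and the procedure paragraph therefore conflict directly, and the LS7 definition sides with the schedule.

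**2. Does anything provided resolve it?** No. The biospecimen section is silent on fasting. The LS7 definition says its criteria are adapted from AHA standards but prints no glucose cut-offs and no rule for non-fasting values. No fasting instruction appears in the text provided.

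**3. Weight of glucose in the score.** 7 components × 2 points = 14, so glucose contributes 0 to 2 of 14. One category is 1 point.

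**4. The plan's own power figure.** Inputs from the Power Statement: 16 churches, average 10 participants each, 80 per group, ICC 0.01, CoV 0.50, SD 2, difference 1.0, 5% type-I error (taken as two-sided, which the plan does not state).

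- Design effect = 1 + [(1 + 0.50²) × 10 − 1] × 0.01 = 1.115
- SE = √(2² × 1.115 × 2 / 80) = 0.334
- Power = Φ(1.0/0.334 − 1.96) = 0.850, against 85% stated
- Recruitment = 160 / (1 − 0.20) = 200, as stated

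The glucose wording enters none of these inputs, so the stated calculation stands.

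**5. Illustrative shift in the mean.** Let d be the net difference in the proportion misgraded by one category, either between groups at Time 3 or between visits within a group. The expected shift is d × 1 point. The values of d are assumptions; the documents give none.

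- d = 0.05: 0.05 points, 5% of the 1.0 target
- d = 0.10: 0.10 points, 10% of the target
- d = 0.20: 0.20 points, 20% of the target
- d = 0: no shift

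Because this is an expected value, it does not require misgrading to be independent between participants or churches.

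**6. Illustrative effect of noise alone.** Suppose misgrading adds independent noise to the LS7 change, over and above the planned SD of 2. The SD becomes √(4 + extra²). With the same design effect, an extra SD of 0.25, 0.5, 0.75 or 1.0 gives power of 84.4%, 82.8%, 80.1% or 76.4%. These extra SDs are also assumptions, and no power loss is claimed.

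**The case against.** The case against making much of this has several parts.

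- **It may be a slip.** One word in one paragraph is at odds with the schedule, and staff might fast participants anyway. That is possible, but the paragraph is the operational text. Its body also mentions only a baseline assessment. Read that way, baseline would be random and 6 months fasting, which is the between-visit difference that would bias the paired tests.
- **The LS7 definition is not airtight.** The word fasting there could modify only the lipid panel. This is fair, but the conflict between the schedule and the procedure paragraph does not depend on it.
- **No cut-offs are printed.** How often a random value would be graded differently, and in which direction, cannot be established. This stands. Confidence attaches to the contradiction, not to the size of its effect.
- **Differential fasting by group is conjecture.** The same procedure and schedule apply to both groups, and churches knowing their assignment is not evidence that fasting would differ. This also stands; the bias is conditional.
- **The illustrated shifts only return what was assumed.** True. They translate an assumption to the scale of the target. One participant moved by one category changes a group mean of 80 by only 1/80 = 0.0125.
- **Fasting instructions may sit elsewhere.** Consent pages and some other material were not available. Such an instruction would not remove the conflict between the schedule and the procedure paragraph.

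**Conclusion.** The concern holds. The protocol specifies random glucose in its visit procedure and fasting glucose in its schedule for the same two visits, and its primary endpoint definition, on its natural reading, uses fasting glucose. Followed literally, the procedure paragraph produces values that do not meet the endpoint definition for one of seven components.

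The numerical effect is unknown. It depends on which instruction staff follow, on grading criteria not printed in the plan, and on whether fasting state differs between groups or visits. With equal net misgrading in both groups, the between-group mean is not shifted by this route, although noise and dilution remain possible. The sample size and the stated 85% power are unaffected as calculations; achieved power would fall only if misgrading raised the SD of change above the assumed 2. This should be fixed because it concerns the primary score.

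**What to change.** Reconcile the health assessment paragraph with the Schedule of Assessments and the LS7 score definition, so that one glucose collection condition applies at Time 1 and Time 3 in both groups. State the LS7 glucose grading criteria that go with that condition. In the same edit, align the lipid panel wording: the procedure paragraph omits the fasting condition that the schedule and the LS7 definition state. That is an omission rather than a contradiction.

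Two additions are optional. Record time since last intake at each assessment, and report a sensitivity analysis of the score without glucose (14 − 2, so 0 to 12 points). All participants should stay in the primary 0 to 14 score.

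The cost is protocol wording, plus one data field if time since intake is recorded. Sample size, stated power and the primary score range do not change.
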